### Trial arm sizes.

Control	EPA	HMB	HMB+EPA	Total
20	17	18	18	73

Some specific measurements were not possible due to patient refusal, patient transfer, or care withdrawal by the attending physician. Therefore, besides providing sample medians (interquartile ranges), sample sizes (n) are also given in the following table of descriptive statistics and p-values testing for differences between the 4 trial arms:

Location	Variable	Control	EPA	HMB	HMB+EPA	p-value
Diaphragm	Force after treatment	5.7 (3.7, 8.0) n=13	5.4 (3.5, 6.7) n=10	4.0 (3.5, 6.0) n=9	6.0 (3.9, 8.3) n=12	0.63
	Change in force	1.3 (0.0, 1.7) n=13	0.1 (-1.4, 3.2) n=10	1.5 (0.0, 3.2) n=9	0.7 (-1.8, 3.7) n=12	0.93
	% change in force	19 (0, 40) n=13	2 (-35, 128) n=10	58 (0, 75) n=9	19 (-24, 100) n=12	0.87
	% change in size	5.0 (0.0, 8.0) n=15	5.0 (0.0, 11.0) n=11	6.0 (0.0, 11.0) n=12	3.0 (-5.5, 16.0) n=12	0.97
Quadriceps	Force after treatment	4.6 (1.8, 11.6) n=17	3.4 (1.7, 11.0) n=13	4.0 (1.0, 9.5) n=11	4.6 (1.5, 6.5) n=13	0.80
	Change in force	1.0 (0.1, 3.7) n=17	0.3 (-0.4, 2.4) n=13	0.5 (-5.0, 3.2) n=11	0.1 (-1.1, 2.2) n=13	0.57
	% change in force	61 (0, 125) n=17	18 (-28, 62) n=13	51 (-50, 118) n=11	6 (-42, 63) n=13	0.72
	% change in size	1.0 (-14.0, 15.0) n=17	-6.0 (-17.0, -1.0) n=13	-12.0 (-23.0, 6.0) n=11	4.0 (-14.5, 14.0) n=13	0.35

Changes are from before to after treatment.

Median (interquartile range) is presented instead of mean (standard deviation) due to outliers.

p-values come from Kruskal-Wallis tests, the non-parametric alternative to one-way ANOVA

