**Effect of EPA and HMB on Strength in ICU Patients**

**NCT01270516**

**3-12-21**

**Statistical Analysis**

## Statistical Analysis

Non-parametric ANOVA testing was used to compare variables (e.g. changes in diaphragm twitch) across the four experimental groups, with post-hoc testing (Tukeys) to determine significance of differences. A p value of less than 0.05 was taken as indicating statistical significance for comparisons.

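### The SAP compares arms without covariate adjustment although day-1 force is implied for every analysed force patient: the tests are valid, but some precision and any between-arm estimate are lost

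*SAP*

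**What the plan says.** The SAP's Statistical Analysis section states: "Non-parametric ANOVA testing was used to compare variables (e.g. changes in diaphragm twitch) across the four experimental groups". It then names Tukey post-hoc testing and a significance threshold of p below 0.05. The note under the results table (Trial arm sizes) adds: "p-values come from Kruskal-Wallis tests, the non-parametric alternative to one-way ANOVA". Neither document mentions a covariate, stratification or any other baseline adjustment, and no day-1 values are shown by arm.

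The table has eight rows. For each muscle it gives force after treatment, change in force, % change in force and % change in size, each with one four-arm p-value. "Changes are from before to after treatment", and the protocol (sections 2 and 3) places these two measurements on days 1 and 11. For control, diaphragm force after treatment reads "5.7 (3.7, 8.0) n=13" and change in force reads "1.3 (0.0, 1.7) n=13". The quadriceps entries are "4.6 (1.8, 11.6) n=17" and "1.0 (0.1, 3.7) n=17". On the choice of summary, the SAP says: "Median (interquartile range) is presented instead of mean (standard deviation) due to outliers".

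**The concern.** A baseline measured on the same scale as the outcome is usually the best covariate a trial has. Here it was measured, but it enters the analysis only as a subtraction or a divisor. Precision is scarce, with 9 to 13 diaphragm force values per arm.

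Two things follow.

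- **Choice of test.** Whether the post-treatment value or the change score gives the more efficient unadjusted test depends on the day-1 to day-11 correlation (ρ), which is not reported. The protocol's objectives tie the hypothesis to strength after treatment, while the SAP's example is change. The table tests both, and % change as well, and names none as primary. An adjusted day-11 comparison is close to the best choice whatever ρ is.
- **No estimate.** The table gives p-values and within-arm medians but no between-arm difference or interval. From a null result, a reader cannot tell a negligible effect from an imprecise one.

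**Working it through.** The SAP gives no power figure to reproduce, and its p-values cannot be recomputed from medians and interquartile ranges (IQRs).

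**1. Is day-1 force available?** These are the n by arm from the SAP table (control, EPA, HMB, HMB+EPA):

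| | After | Change | % change | Total |
|---|---|---|---|---|
| Diaphragm | 13, 10, 9, 12 | 13, 10, 9, 12 | 13, 10, 9, 12 | 44 of 73 (60%) |
| Quadriceps | 17, 13, 11, 13 | 17, 13, 11, 13 | 17, 13, 11, 13 | 54 of 73 (74%) |

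A change value needs both a day-1 and a day-11 value. Since the counts match in every arm, every patient in the after-treatment row has a day-1 value. The size rows (50 and 54 patients) show only % change. That also needs a day-1 value, but the row-to-row check cannot be made there.

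**2. What range of ρ is plausible?** This is an assumption. As a crude guide, take SD = IQR/1.349, equal variance on both days, and ρ = 1 − Var(change)/(2 Var(post)).

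- Diaphragm: pooled SDs 2.82 (post) and 2.96 (change), so ρ = 1 − 2.96²/(2 × 2.82²) ≈ 0.45.
- Quadriceps: pooled SDs 6.29 and 3.48, so ρ = 1 − 3.48²/(2 × 6.29²) ≈ 0.85.

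The range used is 0.2 to 0.85.

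**3. Linear-model gain.** Relative variances are 1 for post, 2(1 − ρ) for change and 1 − ρ² for adjusted. Post is the better unadjusted analysis below ρ = 0.5, where the ratio of adjusted to better is 1 − ρ². Change is better above it, where the ratio is (1 + ρ)/2. Extra patients are 1/ratio − 1, and interval narrowing is 1 − √ratio.

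| ρ | Ratio | Extra patients | On 44 | Narrower by |
|---|---|---|---|---|
| 0.2 | 0.960 | 4% | 1.8 | 2% |
| 0.45 | 0.797 | 25% | 11.2 | 11% |
| 0.5 | 0.750 | 33% | 14.7 | 13% |
| 0.7 | 0.850 | 18% | 7.8 | 8% |
| 0.85 | 0.925 | 8% | 3.6 | 4% |

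The gain peaks at ρ = 0.5. The covariate costs one degree of freedom, about 2 to 3% of variance at 44 to 54 patients.

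**4. Simulated power.** Settings: normal data, diaphragm n, a shift in the HMB arm only, α = 0.05, 20,000 runs per cell (2,000 at ρ = 0.5). Entries are Kruskal-Wallis on post / Kruskal-Wallis on change / rank ANCOVA, in %.

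| ρ | 1 SD shift | 0.5 SD shift |
|---|---|---|
| 0.2 | 50 / 32 / 53 | 15 / 10 / 16 |
| 0.45 | 50 / 46 / 61 | 14 / 14 / 18 |
| 0.5 | 51 / 51 / 63 | not tabulated |
| 0.7 | 50 / 74 / 79 | 14 / 21 / 24 |
| 0.85 | 50 / 97 / 96 | 14 / 43 / 42 |

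Across repeat runs, rank ANCOVA differs from the better unadjusted test by about −1 to +13 points for 1 SD and about −2 to +5 points for 0.5 SD. At the quadriceps n and ρ = 0.85, the change test and rank ANCOVA give 99.1% and 98.8% (1 SD), and 52.7% and 51.6% (0.5 SD), so there is no gain. With a common ρ, the null error of rank ANCOVA was 4.5 to 5.3%.

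**5. What an interval would show.** For 9 HMB against 13 control patients, 95% intervals from inverting the rank-ANCOVA contrast covered 94.6 to 95.5% in simulation. With normal data their median width was 1.73, 1.60 and 0.98 SD at ρ = 0.2, 0.45 and 0.85. At SD 2.82 that is about ±2.4, ±2.3 and ±1.4 in the table's diaphragm force units, against arm medians of 4.0 to 6.0. No adjusted effect itself can be computed from the documents.

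**The case against.** The strongest reply is that this is an efficiency point and not a defect. Unadjusted tests are valid under randomisation, and the post-treatment test answers the protocol's hypothesis as worded. For the quadriceps, where crude ρ is about 0.85, the change test already does as well. All of this stands, and it limits the point to a modest improvement.

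Three stronger readings are tempting but not supported:

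- **Baseline is unused.** Six of the eight rows use day 1 by subtraction or division, and Tukey testing is named beside Kruskal-Wallis (no Tukey result is tabulated). Only covariate adjustment is absent.
- **Day-1 force was imbalanced.** Median after treatment minus median change for the diaphragm is 4.4, 5.3, 2.5 and 5.3, which might suggest a weaker HMB arm at entry. A difference of medians is not a baseline median, so this is only a reason to show day-1 values.
- **Rank ANCOVA would be unsafe.** With the crude per-arm ρ values, its null error reaches 6.3% (diaphragm) and 8.7% (quadriceps), against 4.6% and 4.8% for post. Those per-arm values are very noisy. With a common ρ, a spread as wide as the one observed arises in 62% of simulations for the diaphragm and about 35% for the quadriceps. Unequal correlation is not shown, though it is a limit to state.

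It is also fair to object that a test chosen after results are known should not displace the stated ones. The fix therefore adds to them.

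**Conclusion.** The point holds as a worthwhile, low-cost improvement. The comparisons use no covariate although day-1 force is implied for all 44 and all 54 analysed force patients. The cost is precision and the lack of any between-arm estimate or interval.

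A reader might infer that the null findings are unsound or could turn positive. The documents do not support that: the smallest of the eight p-values is 0.35, and the tests are valid.

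The gain over the better unadjusted analysis is 4 to 33% more patients in the linear model, largest at ρ = 0.5. For rank-ANCOVA power it runs from none to about 13 points (1 SD shift). These sizes rest on an assumed ρ of 0.2 to 0.85, equal variance on the two days, normal data and a shift in one arm. The simulations address force only. The case for an interval does not depend on ρ.

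**What to change.** - **Add one adjusted comparison for each force outcome.** Fit a rank ANCOVA: ranked day-11 value on arm plus ranked day-1 value, with a 3-df F test. It suits the outliers the SAP mentions. Label it post hoc, because results are already known, and report it beside the Kruskal-Wallis tests, which keep their p-values.
- **Give estimates.** For each active arm versus control, report the day-1-adjusted shift with a 95% interval: the set of shifts of that arm's day-11 values that the same contrast does not reject. Make the three intervals simultaneous (for example Bonferroni, 1 − 0.05/3 = 98.3% each) or state that they are unadjusted for multiplicity.
- **Show baseline.** Give day-1 median (IQR) and n per arm for the analysed patients.
- **Size.** Do the same with the size measure that underlies the tabulated % change, and define that measure for the quadriceps. Protocol section 7 measures four component muscles, but the table prints one figure.

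The cost is added SAP wording, one re-run on data the table implies are held, one degree of freedom and a location-shift assumption for the intervals. It does nothing for the patients without day-11 force: 29 of 73 for the diaphragm (73 − 44) and 19 of 73 for the quadriceps (73 − 54).
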